#### ***Secondary Objectives:***

*Objective #2:* To evaluate the safety of SLIT regimen administered over the study period.

#### ***Purpose and Expectations:***

Through Objective #2, we will determine the percentage of adverse events (AE) and serious adverse events (SAE) due to peanut SLIT dosing. There will be a particular focus on symptoms that require treatment and/or hospitalization, symptoms that may lead to poorer compliance, and gastrointestinal symptoms suggestive of eosinophilic disease. We expect that SAEs will be extremely rare. We expect AEs to be more common but to be mostly comprised of transient oropharyngeal itching that does not affect compliance. We expect symptoms of GI and eosinophilic disease to be rare as very little peanut is ingested by the GI route with peanut SLIT

*Objective #3:* To study the changes in immune parameters over time and compare these changes among subjects who were successfully desensitized vs. those who failed. Changes coinciding with the loss of desensitization would also be studied.

*Purpose and Expectations:*

Through Objective #3, we will seek to understand the molecular processes by which SLIT affects the immune system through evaluation of immune mechanisms in relationship to clinical findings of desensitization. We will delineate the impact of peanut SLIT on the subsequent cellular and humoral responses to peanut protein: 1) peanut specific IgE, IgG, and IgG4 response, 2) peanut specific basophil activation, 3) mast cell responses through skin prick testing, and 4) specific T-cell cytokine responses and T regulatory cell (TReg) activation. We anticipate that the effect of peanut SLIT will occur by induction of TRegs, conversion of T cells from an allergic (Th2) to a non-allergic (Th1) lymphocyte response (measured by cytokines, antibody levels, and skin prick test size), a change in peanut-specific basophil activation, or through a combination of the above.

Based on mechanistic studies of subcutaneous immunotherapy for allergic rhinitis[29], OIT for food allergies [12], and our previous work with SLIT for peanut allergies[23], our expectation is that the immunoglobulin response will change over time resulting in a decrease in peanut-specific IgE and an increase in peanut-specific IgG and IgG4. We anticipate an increase in TReg specific cytokines, such as IL-10 and TGF-beta, that will parallel early clinical responses and indicate immune deviation toward tolerance. The conversion from Th2 to Th1 cytokine responses would have a similar clinical effect of making a subject less sensitive to peanuts, but this would likely occur through an alternative mechanism or a mechanism combining TReg activation with other T cell changes. A change in basophil activation would indicate that subjects would be less sensitive to peanut, and we anticipate that response would be in parallel to the finding of clinical desensitization but may not indicate clinical tolerance development. Overall, we will assess these immune parameters over time and in conjunction with clinical levels of reactivity to determine which mechanism(s) is relevant for effective peanut SLIT in desensitization and ultimately the maintenance or loss of desensitization.

*Objective #4:* To evaluate association of baseline characteristics with desensitization as assessed by the 48th month DBPCFC and with loss of desensitization as assessed by the final DBPCFC.

*Purpose and Expectations:*

Preliminary data using peanut SLIT suggested a range of responses to treatment. Through objective #4, we will seek to identify characteristics such as demographics and specifics about the subject's allergy history that may predict a positive response to treatment and in the future allow providers to target treatment to appropriate patients.

## STUDY DESIGN

This SLIT study is a prospective, randomized, open-label study based on previous experience at Duke University Medical Center using OIT and SLIT in food allergic subjects. The study will enroll 55 participants with peanut allergy with a goal of 50 children completing protocol interventions. Upon enrollment, all subjects will undergo an entry DBPCFC with 1000 mg of peanut protein to confirm the peanut allergy diagnosis and establish a baseline threshold level. Following a positive DBPCFC, each subject will begin the study drug with peanut SLIT at a starting dose of 1 pump of a 1/100 dilution of peanut concentrate (2500 mcg peanut protein). During the build-up phase which lasts approximately 20 weeks (Table 1), subjects will dose daily and increase the number of pumps every 1-2 weeks as per the dosing schedule. Subjects return to the research unit for observed dosing with each change in peanut SLIT dilution (1/100, 1/10, full concentration) and with every other dose increase on full concentration until the maintenance dose of 16 pumps of full concentration peanut SLIT (4000 mcg peanut protein) is achieved. Subjects will then continue daily administration of the maintenance dose and return every 6 months for follow-up.

After at least 48 months of peanut SLIT study drug, subjects will undergo a second DBPCFC to 5000 mg of peanut protein to assess desensitization.

- Subjects who are not desensitized are those who are not able to consume more than the MCRT without symptoms, which has been defined as 300 mg of peanut protein. Subjects who consume less than 300 mg of peanut protein without symptoms will stop peanut SLIT and conclude the study. These subjects will not undergo any additional study procedures including the remaining protocol DBPCFCs and will be recommended to resume a strict peanut avoidance diet.
- Subjects who are able to consume more than 300 mg of peanut protein will be randomized to an interval between 1 and 17 weeks during which all peanut including peanut SLIT study drug will be discontinued. This period of avoidance will be followed by a third DBPCFC to 5000 mg of peanut protein to evaluate for the loss of the desensitization effect. After this final DBPCFC, the study will be completed for these subjects. At the primary investigators clinical discretion, they will be recommended to transition to a daily peanut food equivalent to maintain the desensitized effect.

## 2.2 Study Endpoints

### 2.2.1 Primary Endpoint

The primary efficacy endpoints are:

- An estimate of the dose as assessed by the 48th month DBPCFC, also called population sensitization threshold, predicted to provoke reactions in 5% and 10% of the peanut-allergic population. This will also give population level NOAEL and LOAEL that would define interval of consecutive administered dose levels within which the population sensitization threshold lies.
- Multiplicative or differential change in the population sensitization threshold as assessed by the 48th month DBPCFC with a unit change in covariates.
- An estimate of time to loss of desensitization for the following events:

- Subject's true sensitivity threshold to reduce by half, also called half-life of sensitivity threshold.
- Subject's true sensitivity threshold to maintain at the same level of LOAEL.
- Subject's true sensitivity threshold to drop by at least one level of LOAEL.
- Subject's true sensitivity threshold to remain at or above MCRT.
- Estimates of the proportion of patients at a fixed time for any of the above events that define loss of desensitization (bullet 2).
- Multiplicative change in hazard of loss of desensitization with a unit change in covariates.

### **2.2.2 Secondary Endpoints**

Secondary efficacy endpoints include:

- Comparative estimates of changes in immune parameters over time among subjects who were induced with clinical desensitization versus those who failed. Changes coinciding with the loss of desensitization would also be studied.
- Incidence of all adverse events and serious adverse events during the study.
- Incidence of all gastrointestinal and possible gastrointestinal eosinophilic adverse events.

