***11-2308 TLC Subjects - Home Maintenance Dosing – Before Desensitization DBPCFC***

After completing the escalation schedule, subjects will continue to administer 4000 mcg of peanut SLIT daily at home and return to the clinical research unit for follow-up visits every 6 months or more frequently for new or significant symptoms. All subjects will undergo a 5000 mg peanut protein DBPCFC after at least 48 months to verify desensitization which will be defined as a reaction threshold > 300 mg of peanut protein.

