**5.6 Double Blind Placebo Controlled Food Challenge (DBPCFC)**

Protocol DBPCFCs will be conducted on the clinical research unit at entry, after at least 48 months, and after avoidance of peanut SLIT study drug for a randomly selected interval 1 to 17 weeks. Prior

to the food challenge, subjects will be asked to restrict the use of antihistamines (for 5 half-lives of the drug), beta-agonists (12 hours), theophylline (12 hours), and cromolyn (12 hours).

Before each challenge, the subject will have a physical exam and peak expiratory flow measurements performed if the subject is able to reproduce reliable peak expiratory flow measurements prior to the beginning of the challenges.

The DBPCFC consists of 2 parts. A representative from [name] laboratory will randomly determine the order of the 2 parts and prepare all challenge materials. One part will consist of graded doses of peanut flour given every 10-20 minutes up to a cumulative dose of 1000 mg peanut protein (25 mg, 50 mg, 100 mg, 250 mg, 575 mg) during the entry challenge. The 48 month desensitization challenge is 5000 mg (100 mg, 200 mg, 500 mg, 800 mg, 1300 mg, 2100 mg) of peanut protein. The randomly assigned post-avoidance DBPCFC will be identical to the 48 month DBPCFC. The other part of each challenge will consist of identical graded doses of placebo in the form of oat flour.

All food challenges will be administered in a graded fashion to assure safety of subjects. There will be a minimum 10 minute observation period between doses to monitor for symptoms. All food challenges will be performed under physician supervision. The challenge will be administered by a nurse or physician who is blinded to the testing material. The supervising investigator will also be blinded to testing material.

After each challenge the subject will be observed for a minimum period of 1 hour. Reactions will be scored using a Food Challenge Symptom Score sheet. If the subject begins to have clinically significant or persistent subjective symptoms, the food challenge will be terminated and the subject will be given appropriate treatment. Subjects who are symptomatic are observed for a minimum of 2 hours after the challenges are completed before being discharged from the clinical research unit.

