## **8. STATISTICAL CONSIDERATIONS**

For full description of statistical considerations, please refer to the statistical analysis plan. A summary of the plan is described below. Unless otherwise indicated, all statistical tests will be 2 sided and tested at a significance level of 0.05. Corresponding 95% confidence intervals will be presented for statistical tests.

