### **8.1 Study Endpoint Assessment**

#### **8.1.1 Primary Endpoint**

The primary endpoint is defined in Section 2.2.1. First, an Interval-Censoring Survival Analysis (ICSA) approach will be used to analyze the 48th month DBPCFC threshold data (Collett, 1993, Chapter 9, Taylor et al - 2009). Parametric (Log-normal, Weibull) and non-parametric dose-distribution model will be used to estimate the ED10 and the ED05, the doses predicted to provoke reactions in 10% and 5%, respectively, of the peanut-allergic population. Second, for each dose interval bounded by the NOAEL and LOAEL of the 48th month DBPCFC, we will conduct survival analysis with case-1 censoring (Huang – Wellner lecture notes, Kosorok et al, 1998) to estimate time to loss of desensitization.

Sample size was originally calculated for 80% power of detecting a p-value of 0.05 considering 2:1 placebo:peanut SLIT randomization and estimating a 50% pass rate for those randomized to placebo versus a 90% pass rate for those randomized to continue peanut SLIT . Adjusting for an estimated 10% drop out rate resulted in a minimum required sample size of 50 subjects. The sample size for the amended study has not been revised from the estimated minimum required size of 50 subjects since the study is in progress with an existing enrollment of 51 subjects. We intuitively think this number is adequate with the amended study design and analytical methods for the revised primary outcome of interest. However, to confirm our understanding, we plan on conducting simulations to study the power-sample size curve at 80% power based on study assumptions as discussed in the statistical methods section of the statistical analysis plan.

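### The immune-parameter endpoint reduces the seven-level month-48 challenge result to desensitized versus failed at 300 mg, and no planned model relates immune change to the full threshold

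*Protocol*

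**What the plan says.** Protocol 2.2.2 lists as a secondary endpoint "Comparative estimates of changes in immune parameters over time among subjects who were induced with clinical desensitization versus those who failed". SAP 3.2.1 repeats it. Protocol 5.5 says that the month-48 challenge is done "to verify desensitization which will be defined as a reaction threshold > 300 mg of peanut protein", and SAP section 4 uses the same cut.

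The challenge is graded. Protocol 5.6 states: "The 48 month desensitization challenge is 5000 mg (100 mg, 200 mg, 500 mg, 800 mg, 1300 mg, 2100 mg) of peanut protein". SAP 4.2 has the same doses.

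Under Objective #3 (protocol 2.1) the stated purpose is to "assess these immune parameters over time and in conjunction with clinical levels of reactivity to determine which mechanism(s) is relevant".

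Two models are planned:
- **Month-48 threshold.** An interval-censored model uses the full threshold (SAP 10.1). Its covariates are baseline and clinical ones; under the clinical heading SAP 9.3 lists initial skin-test size and initial IgE.
- **Immune change.** The MMRM in SAP 10.2 has terms for population source, center, study week, baseline and baseline by week. Its contrast of interest is challenge weeks against baseline. It has no term for response group or threshold.

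**The concern.** The split pools a child who reacts just above 300 mg with one who tolerates all 5000 mg. In these documents 300 mg is the minimal clinically relevant threshold and the gate to the avoidance phase. No reason is given why it should also be the scale for finding immune correlates.

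The protocol expects the population to be desensitized above that threshold (section 2.1, Purpose and expectations). Its figure of about 45 children eligible for randomization (section 5.2) allows for dropout and makes no allowance for month-48 failures. Both suggest a small failed group. A comparison with few children on one side could miss a marker that does track response, and the null result could then be read as evidence that the mechanism is not involved.

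**Working it through.** **Stated sample size.** The plan gives no power for this endpoint. Its only sample-size figure belongs to the superseded two-arm design: "Sample size was originally calculated for 80% power of detecting a p-value of 0.05 considering 2:1 placebo:peanut SLIT randomization", "estimating a 50% pass rate for those randomized to placebo versus a 90% pass rate for those randomized to continue peanut SLIT". The pooled proportion is (0.9 + 2 × 0.5)/3 = 0.633. The n on SLIT is [1.96 √(1.5 × 0.633 × 0.367) + 0.842 √(0.09 + 0.25/2)]² / 0.4² = 14.96, so 15. The total is 15 + 30 = 45, and 45/0.9 = 50. This matches the plan but says nothing about the immune endpoint.

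**Challenge results.** Cumulative doses are 100, 300, 800, 1600, 2900 and 5000 mg. With reaction at the first dose, that makes seven ordered results.

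**Inputs.** From the documents: 45 children (protocol 5.2) and the rule that "all statistical tests will be 2 sided and tested at a significance level of 0.05". Assumed, because the documents are silent:
- a failure share q of 5 to 30%;
- a correlation ρ between immune change and log threshold, mainly 0.4;
- a normal log threshold with SD 1.0 to 2.0;
- one change score per child.

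**What the cut keeps.** Splitting a normal variable at share q multiplies its correlation with another variable by φ(z_q)/√(q(1−q)). At q = 0.10 this is 0.1755/0.3 = 0.585, and 0.585² = 0.34. In information terms, 45 children count as about 15.

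**Hand check at ρ = 0.4.** Power ≈ Φ(√42 × atanh(r) − 1.96), where r is 0.4 times the factor. With no cut, √42 × 0.4236 = 2.745 and power is Φ(0.785) = 0.78.

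| Failed share | Factor | r | Hand check | Simulated two-group test | Simulated seven-level trend |
|---|---|---|---|---|---|
| 5% | 0.473 | 0.189 | 0.24 | 0.19–0.20 | 0.63–0.76 |
| 10% | 0.585 | 0.234 | 0.34 | 0.32–0.34 | 0.71–0.77 |
| 20% | 0.700 | 0.280 | 0.46 | 0.45–0.48 | 0.73–0.77 |
| 30% | 0.759 | 0.304 | 0.53 | 0.53–0.55 | 0.75–0.76 |

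The simulations compare a pooled t-test with a linear trend on levels 0 to 6; ranges run over the SD. Trials with fewer than two failures count as no detection, so the 5% row falls below the hand check. The chance of 0 or 1 failure among 45 is 0.9⁴⁵ + 45 × 0.1 × 0.9⁴⁴ = 0.052 at q = 0.10, and 0.335 at q = 0.05.

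**Other correlations** (two-group test versus rank correlation over seven levels):
- ρ = 0.3: 0.20 versus 0.46 at 10% failing; 0.34 versus 0.48 at 30%.
- ρ = 0.5: 0.48 versus 0.90 at 10%; 0.65 versus 0.91 at 20%; 0.75 versus 0.91 at 30%.
- ρ = 0.4 with an even split: 0.59 versus 0.72.

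**Where the boundary falls.** The table counts as failed only children tolerating less than 300 mg cumulative. The documents do not settle this:
- The Synopsis assigns a child at exactly 300 mg both to stopping and to randomization.
- The Study Design section has such a child not desensitized, yet gives neither the stopping nor the randomization rule for that result.
- Protocol 5.5 requires more than 300 mg.
- SAP 4.3 requires no symptoms at 300 mg.

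If the 300 mg cumulative step also counts as failed, the failed share becomes Φ(z_q + ln(800/300)/SD). With q = 0.10 that is Φ(−1.282 + 0.490) = 21% at SD 2 and Φ(−1.282 + 0.981) = 38% at SD 1. Over the same range of q, two-group power at ρ = 0.4 is then about 0.37 to 0.58. The trend does not use the boundary and is unchanged.

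**Analysis set.** SAP 10.2 and protocol 8.1.2 limit secondary efficacy to ITT, which SAP section 7 defines as randomized patients. SAP 4.3 randomizes only children who achieve the 300 mg threshold. Read literally, the failed group is outside the set in which it is to be compared.

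**The case against.** Three stronger readings are tempting, and the documents support none of them.

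**That the split will be about 5 against 40.** The only stated rate near this, "a 90% pass rate for those randomized to continue peanut SLIT", comes from the abandoned two-arm design and is not the share exceeding 300 mg at month 48. The expectation about the population carries no percentage, and under Objective #4 the protocol itself reports a range of responses.

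**That real correlates will usually be missed.** Two-group power passes one half at 30% failing with ρ = 0.4, and at 20% failing with ρ = 0.5. At ρ = 0.3 the seven-level analysis also misses about half.

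**That all variation above 300 mg is thrown away.** Protocol 2.2.2 adds that changes coinciding with loss of desensitization will be studied, and the primary model relates initial IgE and skin-test size to the full threshold. What is missing is narrower: change in immune parameters over time against the month-48 level. The added sentence has no specified analysis.

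Other points are fair. This is an unpowered secondary endpoint, worded as estimation, in a Phase I/II study. The t-test simplifies a repeated-measures design, and a linear relation on the log threshold favours the trend. SAP 3.1.2 describes the groups by clinical tolerance where SAP 3.2.1 says clinical desensitization, so even the grouping is unsettled. These points limit how firmly the size can be stated. They do not supply the missing model, and the ordered analysis had more power in every scenario examined.

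**Conclusion.** The concern holds in conditional form. Seven ordered results become two, and no planned model serves the stated aim of relating immune change to levels of reactivity. At ρ = 0.4 the gain from using all levels runs from roughly 20 points when 30% fail to 40 points or more when 10% or fewer fail. The size rests on an assumed failure share, correlation and threshold spread. The direction did not depend on the failure share or on which 300 mg boundary was used, though it does assume a roughly monotone relation between marker change and threshold. The analysis-set gap needs none of these assumptions.

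**What to change.** In protocol 2.2.2 and SAP 3.2.1 and 10.2, pre-specify an analysis of change in each immune parameter against the ordered month-48 result. Either of two forms will do:
- add the highest tolerated cumulative step (0 to 6) and its interaction with visit to the MMRM; or
- enter immune change as a covariate in the interval-censored log-threshold model already planned.

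Run it in all children with a month-48 challenge, not only the randomized set. Keep the desensitized-versus-failed comparison alongside it. Reconcile the 300 mg wording across the Synopsis, Study Design, protocol 5.5 and SAP 4.3, and the tolerance and desensitization groupings in SAP 3.1.2 and 3.2.1.

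The cost is wording and a small change to one model, with no new visits, samples or patients. The downside is that a trend assumes a roughly monotone relation; a plot by level and the retained two-group comparison would check that.

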### **3. SELECTION AND WITHDRAWAL OF PARTICIPANTS**

#### **3.1 Inclusion Criteria**

Individuals who meet *all* of the following criteria are eligible for study interventions:

1. Age 1 to 11 years, either sex, any race, any ethnicity with a convincing clinical history of clinical allergy to peanut or an *in vitro* peanut-specific IgE [CAP-FEIA] > 0.35 kU/L
2. A positive 1000 mg DBPCFC to peanut protein after enrollment.
3. Written consent from participant's parent/guardian, including assent where indicated.
4. Subjects completing Duke IRB Pro0003579, UNC IRB 11-2301 **Sublingual Immunotherapy for Peanut Allergy: A Randomized, Double-Blind, Placebo-Controlled, Phase I/II Pilot Study with a Whole Peanut Extract, CoFAR4** who do not pass the 164 week (3 years) end of study 10 gm DBPCFC to peanut. Duke IRB approved this enrollment exception.

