### **6.1 Procedures and Monitoring**

All unexpected serious adverse events related to the experimental procedures will be reported to the IRB, Food Allergy Initiative DSMB, and FDA in a manner consistent with 21 CFR 312.32. All other adverse events related to the experimental procedures will also be reported to the IRB and DSMB in an expedited manner if they are Grade 3 and above in severity. Any participant deaths that are likely study related and unexpected would be reported within 24 hours. The investigator will continue to follow or obtain documentation of the resolution course of such an event.

Reactions to study drug dosing will be recorded on a dosing log and will not be reported separately as serious adverse events; allergic symptoms are expected during study drug administration and are not unexpected reportable adverse events. Any reaction that meets the criteria for a serious adverse event will be reported both on the dosing log and on an adverse event case report form.

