### **6.2 Definitions**

#### **6.2.1 Adverse Event (AE) or Medical Event**

An adverse event is a new, undesirable medical event or occurrence or worsening of an existing condition (including an abnormal laboratory finding) in a subject that occurs during and throughout the study, whether or not it is considered to be study related. Adverse events or medical events and toxicities are treatment emergent signs and symptoms.

This includes the following:

1. AEs not previously observed that emerge during the protocol participation, including signs or symptoms associated with peanut allergy that were not pre-existing
2. Complications that occur as a result of protocol-mandated interventions
3. If applicable, AEs that occur prior to study-group assignment associated with medication washout, or other protocol-mandated intervention
4. Preexisting medical conditions (other than the condition being studied) judged by the investigator to have worsened in severity or frequency or changed in character during the protocol.

Potential adverse reactions seen in subjects receiving peanut SLIT and subjects undergoing DBPCFC include the following: skin manifestations such as pruritus, urticaria, or angioedema; respiratory symptoms such as wheezing, coughing, nasal congestion/rhinorrhea, cough and hoarseness; and gastrointestinal symptoms such as vomiting, diarrhea, or abdominal pain. Anaphylaxis is a potential risk involving any of the above symptoms plus hypotension and circulatory collapse.

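### The adverse-event and gastrointestinal endpoints pool deliberately provoked food-challenge reactions with SLIT reactions, and no text says that dosing-log reactions are counted

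*Protocol*

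**What the plan says.** - **Endpoint.** Protocol 2.2.2 lists the "Incidence of all adverse events and serious adverse events during the study" and, separately, the incidence of gastrointestinal and possible eosinophilic events. It gives no start point, attribution, counting unit or denominator.
- **Objective.** Under Objective #2 (Protocol 2.1), "we will determine the percentage of adverse events (AE) and serious adverse events (SAE) due to peanut SLIT dosing". The same paragraph expects AEs to be mainly brief oropharyngeal itching and gives particular attention to gastrointestinal symptoms.
- **AE definition.** Protocol 6.2.1 covers an event that "occurs during and throughout the study, whether or not it is considered to be study related". It includes "Complications that occur as a result of protocol-mandated interventions" and, where applicable, "AEs that occur prior to study-group assignment associated with medication washout, or other protocol-mandated intervention". It names reactions in children undergoing DBPCFC among the potential adverse reactions. The same section also describes AEs as treatment emergent, without defining the term.
- **Entry.** Protocol 3.1 requires "A positive 1000 mg DBPCFC to peanut protein after enrollment". The Study Design section fixes the order: "Following a positive DBPCFC, each subject will begin the study drug with peanut SLIT".
- **Recording.** Protocol 6.1 states: "Reactions to study drug dosing will be recorded on a dosing log and will not be reported separately as serious adverse events". Reactions meeting the criteria for a serious adverse event (SAE) go on both the log and an AE form.
- **Relatedness.** Protocol 6.3.1 uses one associated category for the test product and/or the procedure.
- **SAP.** Section 3.2.1 lists only SAE incidence. Section 3.2.2 names AEs, laboratory tests, vital signs and examination. Section 3.1.2 limits the safety objective to the initial 48 months. No section gives a safety estimator or a rule for the dosing log.

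**The concern.** The objective is about one cause, SLIT dosing. The endpoint counts every cause, including up to three procedures that deliberately expose an allergic child to peanut. A total of that kind moves with how many children react at challenge, which is the efficacy outcome, as well as with how SLIT is tolerated. The gastrointestinal endpoint has the same weakness: section 6.2.1 lists vomiting, diarrhea and abdominal pain as possible reactions to SLIT and to the challenge alike, yet Objective #2 wants such symptoms as a treatment signal.

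Meanwhile the commonest expected reaction to treatment is held in a separate record whose place in the analysis is not stated. Two analysts following the text could report very different AE figures from the same data, and neither figure need describe the tolerability of SLIT.

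**Working it through.** The plan states no AE incidence, so there is no figure of its own to reproduce. Its only relevant rate is oropharyngeal itching at 9.3% of doses (Protocol 1.4.1).

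**1. Does the entry reaction count?** Section 6.2.1 points both ways. Its breadth, its item on complications of protocol procedures and its item on pre-assignment events bring the reaction in. The treatment-emergent sentence leaves it out, because the entry challenge comes before the first dose.

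- If it counts, and incidence means children with at least one AE, every analysed child who qualified by the entry challenge has one before any SLIT: n/n = 100%. The exact 95% lower limit is 0.025^(1/n), so 50/50 gives 92.9% to 100% and 51/51 gives 93.0% to 100%. The CoFAR 4 participant, who enters without this study's entry challenge, does not change this, because Protocol 5.2 excludes that child from the data analysis.
- If counting starts at the first dose, the proportion can vary. With n = 50 and assumed proportions of 0, 20, 50 and 80%, the exact 95% intervals are 0–7.1%, 10.0–33.7%, 35.5–64.5% and 66.3–90.0%.

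**2. Does starting at the first dose remove the mixing?** No. The 48-month challenge and the final challenge both follow the first dose, so reactions to them remain AEs. Let s be the share of children with a SLIT AE and r the share reacting at a later challenge. The pooled share lies between max(s, r) and min(1, s + r), and equals 1 − (1 − s)(1 − r) if the two are independent. The documents give neither value. Assuming s = 20% and r = 50%, the pooled share lies between 50% and 70%, and is 1 − 0.8 × 0.5 = 60% under independence. A true 20% would be reported as 50% or more.

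**3. How many dosing reactions have unclear status?** Assume daily dosing for 48 months, no dropout and a constant 9.3%.

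- Doses per child: 48 × 30.4375 = 1,461.
- Itching doses per child: 1,461 × 0.093 ≈ 136.
- For 51 enrolled children: 51 × 1,461 = 74,511 doses, and × 0.093 ≈ 6,930 reactions.

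These are recorded events whose place in the endpoint is undefined, not lost events.

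**4. Would a per-child figure from the log be informative?** If doses are independent, the share of children with at least one itching dose is 1 − (1 − 0.093)^k: 62% at k = 10, 95% at k = 30, and essentially 100% at k = 1,461. If reactions cluster within children, take a beta-binomial model with mean 0.093 and concentration c. The share is then 1 − B(0.093c, 0.907c + 1461)/B(0.093c, 0.907c), which is 16% at c = 0.1, 52% at c = 1 and 93% at c = 5. The values of c are assumptions. A per-child any-reaction figure may therefore saturate even without the entry reaction, so the per-dose rate is needed as the main measure.

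**The case against.** The strongest reply is that this is a descriptive secondary endpoint with a gap in its specification and nothing worse. A reader might infer three stronger things, and the documents do not support them.

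- **That AE incidence is 100% by construction.** This needs both the pre-dose entry reaction to count, against the treatment-emergent sentence, and incidence to mean children with any AE, which section 2.2.2 does not say. The safety population in SAP section 7 (at least one dose) and the SAP's 48-month safety objective, tied to the SLIT regimen, also lean towards counting from treatment. Event counts, per-dose rates, AEs by type or grade, and SAEs are not fixed by the entry criterion.
- **That dosing reactions are excluded.** Section 6.1 sets a recording and reporting route. It does not say that these reactions are not AEs, and Objective #2 treats them as AEs. The silence of SAP 3.2.2 about the log is only silence.
- **That the trial cannot answer its safety objective.** SAE incidence and per-dose rates from the log remain informative, and relatedness is assessed by the investigator (Protocol 6.4).

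Nor are the later challenges bound to end in a reaction. They stop at 5000 mg cumulative (Protocol 5.6), SAP 4.3 caps the final one at the 48-month NOAEL, and the SAP treats no reaction as right-censored.

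All of that stands. It does not remove the mixing. Challenge reactions after the first dose still enter the AE and gastrointestinal counts, and the pooled relatedness category cannot take them out. No sentence brings the log into the incidence.

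**Conclusion.** The point holds as a mismatch between endpoint and objective. As written, the AE and gastrointestinal endpoints do not isolate events due to SLIT dosing, because provoked challenge reactions are pooled in and the status of non-serious dosing reactions is not stated. Protocol and SAP also differ on the endpoint itself: AEs, SAEs and gastrointestinal events in one, SAEs only in the other.

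The size depends on the reading. At the extreme, the any-AE proportion is fixed at 100%; this is one of two readings of section 6.2.1. Counting from the first dose, the distortion depends on the share reacting at later challenges, which the documents do not give. The figure of about 6,930 dosing reactions is illustrative and rests on full adherence, no dropout and a constant rate. The conclusion rests on the wording and not on any of these numbers.

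**What to change.** In Protocol 2.2.2 and SAP 3.2.1 and 3.2.2:

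1. Define treatment-emergent AEs as those from the first SLIT dose, and reconcile section 6.2.1 with that.
2. Make SLIT dosing-related reactions, taken from the dosing log plus AE forms, the measure for Objective #2. Report them mainly as a per-dose rate, separately for build-up and maintenance, with per-child figures by type and grade.
3. Tabulate DBPCFC reactions by challenge (entry, 48-month, final) and keep them out of the SLIT AE and gastrointestinal incidence.
4. Report all other AEs separately.
5. Align the SAP endpoint list and safety window with the protocol.

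The cost is wording in a few sections and one table split. The diaries and dosing log (Protocol 4.4 and 6.1), challenge symptom scores (5.6) and AE forms are already collected, so there is no added burden on the children. The documents do not say whether diary entries are already in analysable form; if not, entering them is the main work.
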